## **2.3 Analysis period and treatment groups**

### **2.3.1 Final Week 52 analysis**

The efficacy and safety analyses will be conducted up to Week 52 or Week 60, when all subjects have completed the study.

The efficacy will be conducted using the following treatment groups:

- AIN457 300mg Q2W (subjects randomized to secukinumab 300 mg every 2 weeks arm)
- AIN457 300mg Q4W (subjects randomized to secukinumab 300 mg every 4 weeks arm)
- PBO-AIN457 300mg Q2W (subjects randomized to placebo who switched to secukinumab 300 mg every 2 weeks arm at Week 16. Data is included after first intake of placebo.)
- PBO-AIN457 300mg Q4W (subjects randomized to placebo who switched to secukinumab 300 mg every 4 weeks arm at Week 16. Data is included after first intake of placebo.)

The safety will be conducted using the following treatment groups:

- AIN457 300mg Q2W (subjects randomized to secukinumab 300 mg every 2 weeks arm)
- AIN457 300mg Q4W (subjects randomized to secukinumab 300 mg every 4 weeks arm)
- Any AIN457 300mg Q2W (subjects randomized to secukinumab 300mg Q2W plus subjects randomized to placebo to secukinumab 300 mg every 2 weeks arm after their first intake of secukinumab)
- Any AIN457 300mg Q4W (subjects randomized to secukinumab 300mg Q4W plus subjects randomized to placebo to secukinumab 300 mg every 4 weeks arm after their first intake of secukinumab)
- Any AIN457 (this group combines the two groups “Any AIN457 300mg Q2W” and “Any AIN457 300mg Q4W”)

The subjects randomized to placebo to secukinumab 300 mg every 2 weeks arm and placebo to secukinumab 300 mg every 4 weeks arm will be counted in placebo until the day before the first secukinumab dose. Subsequently, they will be counted in Any AIN457 300mg Q2W or Any AIN457 300mg Q4W, respectively. AEs that occur starting on the day of taking the first secukinumab dose will be counted in Any AIN457 300mg Q2W or Any AIN457 300mg Q4W; other assessments, (i.e. efficacy, lab assessments) collected on the day of taking the first secukinumab dose will be counted in the placebo group.

Safety tables related to exposure adjustment incident rate will also display the placebo treatment group.

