12.1 Analysis sets

The Randomized Analysis Set (RAS) consists of all randomized subjects. Subjects will be analyzed according to the treatment assigned to at randomization.

The Full Analysis Set (FAS) comprises all subjects to whom study treatment has been assigned. Subjects will be analyzed according to the treatment assigned to at randomization. Mis-randomized subjects (mis-randomized in IRT) will be excluded from FAS. Mis-randomized subjects are defined as cases where IRT contacts were made by the site either prematurely or inappropriately prior to confirmation of the subject's final randomization eligibility and no study medication was administered to the subject.

The Safety Set includes all subjects who received at least one dose of study treatment. Subjects will be analyzed according to the study treatment received, where treatment received is defined as the randomized/assigned treatment if the patient took at least one dose of that treatment or the first treatment received if the randomized/assigned treatment was never received.

For all analysis in Treatment Period 1, the Placebo group to secukinumab 300 mg every 2 weeks and Placebo group to secukinumab 300 mg every 4 weeks will be pooled together.

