## **2.2 Analysis sets**

The following analysis sets will be used for the data analysis.

The **Randomized Analysis Set (RAN)** consists of all randomized subjects. Subjects will be analyzed according to the treatment they are assigned to at randomization. Unless otherwise specified, misrandomized patients (mis-randomized in IRT) are excluded from the randomized set.

Mis-randomized patients are patients who were screen-failures, but had been randomized by the investigator before eligibility was finally assessed, however had not been treated.

Furthermore, all subjects with serious GCP violation at their site will be excluded from the randomized set.

The **Full Analysis Set (FAS)** consists of all subjects to whom study treatment has been assigned. Subjects will be analyzed according to the treatment assigned to at randomization. Mis-randomized subjects (mis-randomized in IRT) and subjects with serious GCP violation at their site will be excluded from FAS. If the actual stratum is different to the assigned stratum in IRT, the actual stratum will be used in analyses.

The **Safety Set (SAF)** includes all subjects who received at least one dose of study treatment. Subjects will be analyzed according to the study treatment received. Treatment received is defined as the randomized/assigned treatment if the subject took at least one dose of that treatment or the first treatment received if the randomized/assigned treatment was never received (subject received the wrong treatment during the entire study). Mis-randomized subjects and subjects with serious GCP violation at their site will be excluded from the safety set.

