- A mixed effects logistic regression model (MELRM) will be fitted. The endpoint is HiSCR at all time points from Week 2 up to Week 52 and are included on the left hand side of the model as dependent variables. The covariates included as fixed effects are: treatment group, visit, baseline AN count and the interaction between visit and treatment group. An unstructured covariance structure will be applied. In case of non-convergence, alternative covariance structures will be considered. If additional convergence issues are encountered, then modifications to the model will be considered.

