## 4 Change to protocol specified analyses

Response of HS-PGA is defined as the achievement of at least a 2-point reduction in HS-PGA score compared to baseline or the achievement of a “mild” status (defined as achieving an HS-PGA score of  $\leq 2$ ). While in the Protocol it is defined as at least a 2-point reduction in HS-PGA score only.

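### SAP 2.3.1 words the placebo efficacy groups as Week 16 switchers and lists no pooled placebo group, which contradicts the FAS, Protocol 12.1 and its own closing paragraph

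*SAP*

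**What the plan says.** SAP 2.3.1 lists four efficacy groups. The active groups are defined by randomization alone, for example "AIN457 300mg Q2W (subjects randomized to secukinumab 300 mg every 2 weeks arm". The placebo groups carry a further condition, as in "subjects randomized to placebo who switched to secukinumab 300 mg every 2 weeks arm at Week 16". Their data count from the first placebo injection, so these groups reach back before the switch. The Q4W placebo group is worded in the same way. No pooled placebo group appears in the efficacy list.

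Four other texts bear on this:

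- **SAP 2.2.** The FAS "consists of all subjects to whom study treatment has been assigned", analyzed by randomized treatment. SAP 2.13 uses the FAS for its efficacy analyses.
- **Protocol 12.1.** For all Treatment Period 1 analysis, the Q2W placebo group and the "Placebo group to secukinumab 300 mg every 4 weeks will be pooled together".
- **SAP 2.3.1, closing paragraph.** Patients randomized to either placebo sequence "will be counted in placebo until the day before the first secukinumab dose". Efficacy assessments made on the switch day are assigned to the placebo group.
- **SAP Section 4.** The only declared change to the protocol's analyses concerns the HS-PGA response: "Response of HS-PGA is defined as the achievement of at least a 2-point reduction in HS-PGA score compared to baseline". Reaching a mild status is added there as an alternative.

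The outputs include the placebo period. For the HiSCR model, "The endpoint is HiSCR at all time points from Week 2 up to Week 52", with treatment group, visit and their interaction as fixed effects. The models for AN count, AN50, flare and NRS30 follow the same pattern.

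**The concern.** Membership of a placebo group from Week 2 onward appears to depend on an event at Week 16, and only on the placebo side. A placebo patient who stops before the switch would lose all observed visits from these outputs, while a secukinumab patient with the same history would keep them. The flare Kaplan-Meier curves show this most plainly, because a placebo patient who flares and leaves before Week 16 would be missing from time zero.

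The two placebo sequences also receive the same treatment until Week 16. Reporting them separately over that period gives two curves for one treatment, each with half the patients.

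At stake is the reading of the Week 2-16 part of the exploratory curves and models, the only placebo-controlled visits they contain. One exploratory objective in SAP Table 1-1, on CRP and ESR, explicitly compares with placebo after 16 weeks. SAP 2.13 summarizes those markers by treatment group, with no pooled placebo group available.

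**Working it through.** **1. One patient under each text.** Take a placebo patient who stops treatment at Week 8 and keeps attending visits, as Protocol Section 8 asks.

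- Group list in SAP 2.3.1, read literally: in no efficacy group at any visit.
- FAS: included, by randomized treatment.
- Closing paragraph of SAP 2.3.1: counted in placebo throughout, because no secukinumab dose is ever taken.
- Protocol 12.1: included in pooled placebo up to Week 16.

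A secukinumab patient with the same history is included under all four. The list cannot be programmed together with the other three texts. The closing paragraph also refers to a placebo group that the efficacy list does not contain.

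**2. The plan's own power.** Inputs (Protocol 12.8; SAP Section 3): N = 471, so 471/3 = 157 per active arm and 157 pooled placebo; HiSCR 30% v 50%, so d = 0.20; two-sided alpha 4% (q2w) and 1% (q4w). With placebo size n, active size kn and p̄ = (p1 + k·p2)/(1 + k), the continuity-corrected two-proportion formula is:

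- n0 = [z(1-α/2)·√(p̄(1-p̄)(1+1/k)) + z(power)·√(p1(1-p1) + p2(1-p2)/k)]² / d²
- n = (n0/4)·[1 + √(1 + 2(1+1/k)/(n0·d))]²

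Solved for power:

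- Pooled placebo (157 v 157, k = 1): 93% for q2w and 82.8% for q4w, against the stated 93% and 83%.
- One half (157 v 78.5, k = 2): 77.7% and 58.5%.

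The stated powers therefore assume pooled placebo.

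**3. Precision against one half.** SAP 1.1 plans about 180 per secukinumab arm and about 180 on placebo in total, so about 90 per sequence (541/6 = 90.2). At 50% v 30%:

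- Pooled: SE = √(0.25/180 + 0.21/180) = 0.0506; half-width 1.96 × 0.0506 = 9.9 points.
- One half: SE = √(0.25/180 + 0.21/90) = 0.0610; half-width 1.96 × 0.0610 = 12.0 points.
- Ratio 0.0610/0.0506 = 1.21.
- Placebo rate alone: 1.96·√(0.21/180) = 6.7 points v 1.96·√(0.21/90) = 9.5 points.

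Averaging the two halves restores the pooled precision: ¼(0.21/90 + 0.21/90) = 0.21/180.

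**4. Selection, if programmed literally.** Let f be the share of placebo patients observed at a visit who never switch, and r their response rate. With 30% overall, the rate among switchers is (0.30 - f·r)/(1 - f). The documents give neither f nor r, so these values are assumptions:

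- f = 3%, r = 20%: 30.3% (+0.3 points)
- f = 5%, r = 10%: 31.1% (+1.1)
- f = 10%, r = 10%: 32.2% (+2.2)
- f = 15%, r = 0%: 35.3% (+5.3)

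In each case placebo looks better and the drug effect is understated. If non-switchers responded better than switchers, the sign would reverse.

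**The case against.** The strongest reply is that the switching condition is only a loose label for the randomized sequence. The switch regimen is allocated at randomization (note to SAP Figure 1-1), so every placebo patient has a sequence whether or not Week 16 is reached. The FAS goes by randomized treatment, SAP Table 5-2 does not exclude anyone for failing to switch, and the closing paragraph of 2.3.1 counts placebo patients by randomized arm. This stands as far as it goes: a reader might infer that the placebo reference is selected on a future event, and the documents do not establish that. They establish that 2.3.1 is inconsistent and that one reading has this effect.

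It also stands that SAP 2.13 names no Week 2-16 contrast against placebo, that both halves stay in the models so a combined contrast could recover the precision, and that two unpooled but complete placebo curves are imprecise rather than biased. With observed data only, patients with no later assessment drop out of later descriptive rates in every arm. The asymmetry is therefore limited to visits at which non-switchers were observed.

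A further argument is that the pooling rule belongs to the Week 16 primary endpoint analysis, whose SAP is separate and not available here. This is weaker. Protocol 12.1 covers all Treatment Period 1 analysis, SAP Section 1 says the data will be analyzed according to protocol Section 12, and these outputs include Treatment Period 1 visits.

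**Conclusion.** The contradiction and the undeclared lack of pooling are in the text on any reading, and they should be corrected. The precision cost is an SE about 21% larger for any Week 2-16 comparison made against a single placebo half at the protocol's assumed rates.

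The selection effect is conditional. It arises only if the list is programmed literally, and its size rests on assumed inputs: 0.3 to 5.3 points over a 3-15% non-switch share and 0-20% response among non-switchers. No established bias should be inferred, and none in favor of secukinumab: if non-switchers respond worse, the drug effect is understated.

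The affected outputs are exploratory: the Week 52 tables and figures, the flare Kaplan-Meier curves and the mixed models. A reader might also infer that the primary result or its power is weakened. The documents do not support that: the confirmatory tests belong to the Week 16 SAP, and the 93% and 83% powers are reproduced with pooled placebo.

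**What to change.** In SAP 2.3.1:

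- Delete the switching condition. Define PBO-AIN457 Q2W and Q4W as FAS patients by the sequence assigned at randomization.
- Add a pooled placebo group for tables and figures through the pre-dose Week 16 assessment.
- In the MELRM and MMRM, keep the assigned sequences as groups and pre-specify a combined placebo contrast for Weeks 2-16. This avoids a group variable that changes within a patient, which would require the models to be respecified.
- After the switch, show the two sequences separately, by assigned sequence. Label any display limited to patients who took secukinumab, because an unlabelled restriction would bring back one-sided conditioning after Week 16.
- Reconcile the closing paragraph with the group list.

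If the sponsor intends separate placebo groups before Week 16, SAP Section 4 should declare this as a departure from Protocol 12.1. The cost is one combined contrast and one extra display group; no new data are needed.

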4.5 Risks and benefits

Secukinumab has demonstrated positive benefit-risk in the treatment of multiple chronic inflammatory indications including moderate to severe plaque psoriasis, ankylosing spondylitis, psoriatic arthritis. Based on the available evidence at the time of this protocol (see [Section 1.1](#) for further details), secukinumab has the potential to also show positive benefit-risk in reducing the extent of inflammation in patients with moderate to severe HS. Given the impact of these inflammatory lesions on the quality of life of patients with HS, a reduction in the number of such lesions could directly benefit patients.

Secukinumab therapy has a well-established and well-described safety profile based on extensive post-marketing experience and continued clinical trial patient exposure since its approval for the first indication of moderate to severe plaque psoriasis. Details of the risk and benefits are outlined in the current version of the Investigator's Brochure.

Observed risks at doses up to 300 mg s.c. every 4 weeks included infections, of which the most frequently reported were upper respiratory tract infections. Oral herpes, oral candidiasis and tinea pedis were also more frequently reported. Most of the infections were non-serious, mild to moderate in severity, clinically manageable and did not lead to treatment discontinuation. Neutropenia and hypersensitivity reactions are also risks observed with secukinumab. Cases of neutropenia were uncommon, generally mild to moderate, transient, did not lead to treatment discontinuation, and only a few cases were temporally associated with non-serious infections.

Secukinumab 300 mg s.c. every 2 weeks is not an approved dose regimen. It has been administered in 7 completed studies in approximately 460 patients with psoriasis and uveitis, with approximately 300 patients receiving continuous treatment for at least 24 weeks. This included over 200 patients with psoriasis. The safety profile observed in the available data is consistent with the known safety profile of secukinumab.

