## 2.6 Safety analyses

All safety analyses will be based on the safety set.

Analysis of adverse events will be based on treatment emergent events, which are defined as events started on or after the first dose of study treatment or events present prior to the first dose of study treatment but increased in severity based on preferred term and on or before last dose + 84 days.

Other safety variables will be evaluated based on on-treatment events, which are defined as any events that happened after first dose of study treatment and on or before last dose + 84 days.

Safety analysis will be performed on actual treatment and the entire study period.

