#### 5.4.3 Exposure-adjusted incidence rate and $100(1 - \alpha)\%$ confidence interval

It will be assumed that for each of  $n$  subjects in a clinical trial the time  $t_j$  ( $j = 1, \dots, n$ ) to the first occurrence of a certain treatment emergent event is observed, or if the event was not experienced, the (censored) time to the end of the observation period or last dose plus 84 days whichever occur earlier. The sequence of first occurrences of an event will be modeled to follow approximately a Poisson process with constant intensity  $\theta$ . The rate parameter  $\theta$  will be estimated as  $\lambda = D/T$ , where  $T = \sum_{j=1}^n t_j$  and  $D$  is the number of subjects with at least one event. Conditionally on  $T$ , an exact  $100(1 - \alpha)\%$  confidence interval for a Poisson variable with parameter  $\theta T$  and observed value  $D$  can be obtained based on (Garwood, 1936), from which an exact  $100(1 - \alpha)\%$  confidence interval for  $\lambda = D/T$  will be derived as follows (Sahai, 1993; Ulm, 1990):

Lower confidence limit  $L = \frac{0.5\chi_{\alpha/2, 2D}^2}{T}$  for  $D > 0$ , and = 0 otherwise;

Upper confidence limit  $U = \frac{0.5\chi_{1-\alpha/2, 2D+2}^2}{T}$ .

where  $\chi_{\alpha, k}$  is the  $\alpha$ -th quantile of the Chi-square distribution with  $k$  degrees of freedom.

The example below shows how this should be handled for cases where subjects switch treatment. In particular for summarizing ‘Any AIN’ as a group, one should take into consideration the sequence of treatments while calculating exposure time for subjects.

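### Week 52 exposure-adjusted AE tables set a placebo rate from about Weeks 0-16 beside secukinumab rates over the whole study; the two are comparable only if the hazard is constant

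*SAP*

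**What the plan says.** SAP 2.3.1 sets the scope of the final analysis: "The efficacy and safety analyses will be conducted up to Week 52 or Week 60, when all subjects have completed the study". Subjects randomized to a placebo-to-secukinumab arm "will be counted in placebo until the day before the first secukinumab dose"; after that they move to the matching Any AIN457 column. Placebo is not among the listed safety groups, but one sentence adds it to one kind of table: "Safety tables related to exposure adjustment incident rate will also display the placebo treatment group".

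SAP 2.6 fixes the period: "Safety analysis will be performed on actual treatment and the entire study period". Table 2-3 (SAP 2.6.1) accordingly has a single row, for the entire study period.

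SAP 5.4.3 defines the rate as D/T. D "is the number of subjects with at least one event", and T sums the time to first event or, without an event, the "time to the end of the observation period or last dose plus 84 days whichever occur earlier". The sequence of first events "will be modeled to follow approximately a Poisson process with constant intensity".

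This SAP contains no adverse-event rate limited to Weeks 0-16, no interval-specific rate, no check of constant hazard, and no note that the columns cover different periods. It also plans no test or rate ratio against placebo.

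**The concern.** Dividing by time at risk removes the effect of unequal follow-up only when the hazard is the same early and late. Here the placebo column is almost all early time, the randomized secukinumab columns mix early and late time, and the Any AIN457 columns add switchers whose drug time starts only after about 16 weeks on study. A difference between columns can therefore reflect calendar position in the study as well as treatment.

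There are reasons to doubt a constant hazard. Protocol 6.1.3 gives weekly injections at the start and less frequent dosing later, so drug exposure changes over time. Counting only first events also depletes susceptible subjects as follow-up lengthens.

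These are the only adverse-event tables that this SAP says will carry a placebo column, so readers will use them to judge excess risk. Protocol 4.5 says "Observed risks at doses up to 300 mg s.c. every 4 weeks included infections"; it also names neutropenia and hypersensitivity reactions.

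**Working it through.** **Plan's own figure.** SAP Table 5-1 has a first exposure of 100 days and events on study days 50 and 110. Placebo time is 50 days; active time is 110 - 100 = 10 days; Any AIN is 10 days. This reproduces the table and confirms that the clock restarts at the switch. (The table's 150 mg dose is not one used in this study; the arithmetic is unaffected.)

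**Assumed inputs, because the documents give no adverse-event rates.** Placebo risk of a first event by Week 16 is 15%. The hazard is h in Weeks 0-16 and f × h afterwards, with the same f in both groups. There is no dropout. The true hazard ratio (HR) is 1.0 or 1.3.

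**Times.** 16 weeks = 112/365.25 = 0.3066 years. Weeks 16 to 52 = 252/365.25 = 0.6899 years.

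**Placebo.** h = -ln(0.85)/0.3066 = 0.530, so the rate is 53.0 per 100 patient-years (PY).

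**Drug, HR 1.0, f = 0.5.**
- Event-free at Week 52: 0.85 × exp(-0.265 × 0.6899) = 0.85 × 0.8329 = 0.7080, so D = 0.2920 per subject.
- Time at risk: 0.15/0.530 + (0.85 - 0.7080)/0.265 = 0.283 + 0.536 = 0.819 years.
- Rate: 0.2920/0.819 = 35.7 per 100 PY. Ratio: 35.7/53.0 = 0.67.

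**Drug, HR 1.3, f = 0.5.**
- Early hazard 0.689, late hazard 0.3445. Event-free at Week 16: 0.8096; at Week 52: 0.8096 × 0.7885 = 0.6383, so D = 0.3617.
- Time at risk: 0.1904/0.689 + 0.1713/0.3445 = 0.276 + 0.497 = 0.773 years.
- Rate: 46.8 per 100 PY. Ratio: 46.8/53.0 = 0.88.

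**Same formulas, other patterns (drug to Week 52, placebo 53.0):**

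| Hazard after Week 16 | Rate, HR 1.0 | Ratio shown | Ratio shown, HR 1.3 |
|---|---|---|---|
| rises 1.5-fold | 69.3 | 1.31 | 1.68 |
| constant | 53.0 | 1.00 | 1.30 |
| falls 1.5-fold | 41.6 | 0.78 | 1.03 |
| falls 2-fold | 35.7 | 0.67 | 0.88 |
| falls 3-fold | 29.6 | 0.56 | 0.74 |

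Running drug follow-up to Week 60 changes the last three HR 1.3 values to 1.01, 0.86 and 0.70.

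**What reversal requires.** For placebo rates of 100 down to 10 per 100 PY, a true 1.3 falls below 1 only if the late hazard is less than 0.61 to 0.66 of the early hazard. For a true 1.5 the limits are 0.43 to 0.51, and for a true 2.0 they are 0.16 to 0.27.

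**Depletion alone.** Take a constant hazard within each subject, gamma-distributed between subjects, and HR 1.3. At 100 per 100 PY with variance 1, the ratio is 1.26 when both groups are followed to Week 16, and 1.01 when drug runs to Week 52 against placebo to Week 16. At 10 per 100 PY, even with variance 2, it is still 1.19 in the planned layout, so uncommon events are little affected.

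**Switchers.** At 100 per 100 PY, HR 1.3 and f = 0.5, the randomized q2w column shows 0.91. Any AIN457 300 mg Q2W (180 plus 90 switchers) shows 0.83 if the hazard follows study time and 0.93 if it follows time on drug.

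**Sampling variation.** In 4000 simulated trials with 180 per arm under those same settings, the secukinumab rate exceeded placebo in 91% with Weeks 0-16 in both groups, but in 32% with the planned table.

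**The case against.** The strongest reply is that Week 16 is analysed elsewhere. This SAP covers only the final analysis, and several places suggest that the separate Week 16 analysis includes safety. Protocol 3 makes a regimen decision turn on benefit-risk at that point. Protocol 12.1 pools placebo for all Treatment Period 1 analyses. SAP 2.14 refers to serious adverse events belonging to the Week 16 analysis. A reader might infer from the Week 52 SAP that the trial has no concurrent Weeks 0-16 adverse-event comparison at all. The documents do not support that, because the Week 16 plan was not supplied. This part of the objection stands and limits the point to the Week 52 exposure-adjusted tables. It does not make those tables like for like, and SAP 2.14 plans only listings of new or changed serious events, not an updated early-period comparison.

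Two further limits also stand. The display is descriptive, with group rates and no planned contrast. And the placebo column is not strictly 16 weeks: placebo subjects who stop without switching can contribute time up to the last visit or last dose plus 84 days.

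A reader might also infer that the tables will hide an excess of infections. The documents do not support that either. They give no hazard pattern, a rising hazard would exaggerate an excess, and reversal needs a marked decline or strong heterogeneity with common events.

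**Conclusion.** The mismatch of periods is certain from the text. Its effect is conditional: no bias under a constant hazard, dilution and possibly reversal under a falling hazard or depletion, inflation under a rising one. The illustrative ratios of 0.67 (no true difference) and 0.88 (true 1.3) rest on an assumed 15% placebo risk by Week 16, a hazard halved afterwards in both groups, and no dropout. The point concerns how the Week 52 exposure-adjusted tables can be read. It does not show a failing of the whole safety evaluation. It is worth correcting because those tables invite a comparison that they cannot support without an unchecked assumption.

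**What to change.** In SAP 2.3.1, 2.6 and Table 2-3, add a Treatment Period 1 row or set of columns, produced from the final database, giving exposure-adjusted rates for AIN457 300 mg Q2W, AIN457 300 mg Q4W and pooled placebo. In all three groups, censor events and time at risk at the day before the Week 16 dose. For subjects who discontinued, censor at a common study-day cut (for example Day 112) or last dose plus 84 days, whichever is earlier. Under the working's piecewise model this layout returns the true 1.30 whatever happens after Week 16.

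In the entire-period tables, footnote the placebo column as covering a different, shorter period and not being a like-for-like comparison. Removing the column is optional.

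The cost is a few extra tables and some SAP wording, with no new data. Protocol 12.1 already pools placebo for this period, and SAP 2.6.3 already plots laboratory data for Treatment Period 1.
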